### 9.1.5 Documentation of Concomitant Medications

Concomitant medication is any drug given in addition to the study drug. These may be prescribed by a physician or obtained by the subject over the counter. At each study visit, subjects will be asked the status of use (drug name, route of administration, treatment period, and treatment purpose) of any medication other than the study drug (including vitamin compound, over-the-counter medication, and Chinese medicine) used from signing of informed consent through the end of the study.

### 9.1.6 Documentation of Concurrent Medical Conditions

Concurrent medical conditions are those significant ongoing conditions or diseases that are present prior to first dose. This includes clinically significant laboratory or physical examination abnormalities noted at baseline examination, according to the judgment of the investigator. The condition (ie, diagnosis) should be described.

### 9.1.7 Questionnaire for Patient Preference for Treatment

Patient preference for treatment interviewed from the subjects using the standardized questions\* at the end of treatment period (treatment selection rate)

\*: Questions

Regarding the drug therapy after the end of this research, which treatment do you select from the following choices from 1 to 4?

1. Either once-weekly DPP-4 inhibitor or daily DPP-4 inhibitor
2. Once-weekly DPP-4 inhibitor
3. Daily DPP-4 inhibitor
4. Neither once-weekly DPP-4 inhibitor nor daily DPP-4 inhibitor

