## 6.0 STUDY DESIGN AND DESCRIPTION

### 6.1 Study Design

#### <Study design>

This is a randomized, open-label, two-way crossover study which aims to examine the patient preference for treatment with once-weekly dosing of DPP-4 inhibitor trelagliptin versus daily dosing of DPP-4 inhibitor alogliptin among the patients with type 2 diabetes mellitus who are being treated with daily dosing of DPP-4 inhibitor.

After obtaining the consent, the subjects who are judged eligible as a result of eligibility check will be randomized either to trelagliptin preceding group (T-A group) or alogliptin preceding group (A-T group).

Planned number of subjects is 60 in total.

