## **9.0 STUDY PLAN**

### **9.1 Clinical study procedure**

The investigators shall collect data in accordance with the procedure below. In principle, all the tests, observations, and evaluations of study subjects shall be performed by the same investigators. The study schedule is provided in Appendix A.

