### 9.3.3 End of Study (VISIT3: Week 16)

The study subjects choose either trelagliptin or alogliptin, or neither of them. If the subjects cannot choose either of them, then the investigators choose the drug for consequent treatment upon adequate explanation.

Tests, observations and evaluations performed at the start of the screening period (Visit 3: Week 16) are shown below.

- Physical examination
- HbA1c
- DTSQ
- Concomitant medication (a)
- Treatment compliance
- Questionnaire for patient preference for treatment

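### The single open-label preference answer is taken by interview at the visit where the next drug is decided, with nothing to guard it from interviewer influence

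*Protocol*

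**What the plan says.** - **Design.** Protocol 6.1: "This is a randomized, open-label, two-way crossover study".
- **Mode of the primary outcome.** Protocol 9.1.7: "Patient preference for treatment interviewed from the subjects using the standardized questions", at the end of treatment. It is one question with four fixed options. SAP 5.1.1 also defines the analysis set by the subject having been interviewed.
- **What is asked.** "Regarding the drug therapy after the end of this research, which treatment do you select from the following choices from 1 to 4" The answer concerns the subject's actual care after the study.
- **Who collects it.** Section 9.1.7 names no interviewer. The general rule in 9.1 is "The investigators shall collect data in accordance with the procedure below", followed by "In principle, all the tests, observations, and evaluations of study subjects shall be performed by the same investigators".
- **What else happens at that visit.** Protocol 9.3.3: "The study subjects choose either trelagliptin or alogliptin, or neither of them". Then: "If the subjects cannot choose either of them, then the investigators choose the drug for consequent treatment upon adequate explanation".
- **What is not said.** Neither document states self-completion, a separate interviewer, concealment of the answer, or an order between the question and the talk about later treatment.
- **Analysis.** SAP 5.1.1 applies Fisher's exact test to a sequence-by-period-preferred table, using only subjects who chose one regimen. Its sensitivity analysis restricts to subjects who took both drugs. SAP 3.4 plans no analysis by institution, and the study summary gives two institutions.

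**The concern.** The primary result rests on one subjective answer from a subject who knows both regimens. On the default reading it is given to a clinician who knows them too, during a visit about what the subject will take next. Fixed wording controls what is asked. It does not control who asks, what was said beforehand, or whether the subject tries to give the answer that seems expected.

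The crossover was chosen to deal with order and the most recent medication (Protocol 4.1 and 6.2). A pull toward one regimen is a different kind of error. In the SAP's table, a pull toward weekly moves T-A subjects into the first-treatment column and A-T subjects into the second-treatment column. That is the pattern the Mainland-Gart test reads as a treatment preference. Neither the planned sensitivity analysis nor any site tabulation would reveal it, and it could not be repaired after the data are in.

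**Working it through.** **1. The plan's own figure.** Protocol 13.3 assumes 60% weekly, 20% daily and 20% no preference, with 90% power, two-sided 5% and 54 subjects.

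- Weekly share among those with a preference: 0.60/0.80 = 0.75.
- Subjects with a preference: 54 × 0.80 = 43.2, about 43.
- The exact binomial test with 43 subjects rejects at 29 or more, or at 14 or fewer. Power at 0.75 is 90.4%.
- Letting the number with a preference vary, 54 subjects give 91.0%.
- 54/0.90 = 60 randomized.

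The sample size reproduces and is not in question. The SAP's actual test, at 27 per sequence, has 89.8% power.

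**2. Set-up for the illustration.** There are 27 evaluable subjects per sequence (54/2). The true null is 40% weekly, 40% daily and 20% no preference, keeping the plan's 20%. Let *w* and *d* be the reported weekly and daily rates, the same in both sequences, with q = w + d and p = w/q.

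Rejection probability = Σ over m₁, m₂ of Bin(m₁; 27, q) · Bin(m₂; 27, q) · Σ over i, j of Bin(i; m₁, p) · Bin(j; m₂, p) · 1{two-sided Fisher p ≤ 0.05}

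Here m₁ and m₂ count the subjects with a preference in each sequence, and i and j count those choosing weekly.

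**3. Why the test does not cancel the shift.** With the same p in both sequences, the odds ratio of the SAP's table is (w/d)². At 40/40 it is 1. At 44/36 it is (44/36)² = 1.49, and at 48/32 it is 2.25. A pure order effect moves both rows toward the same column and leaves the ratio at 1.

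**4. Movement from daily to weekly.** The size and direction are assumptions.

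| Share of daily-preferring subjects moved | Answers moved, of 54 | w/d | False-positive rate |
|---|---|---|---|
| 0% | 0 | 40/40 | 3.2% |
| 10% | 0.10 × 0.40 × 54 = 2.2 | 44/36 | 7.0% |
| 15% | 3.2 | 46/34 | 12.2% |
| 20% | 4.3 | 48/32 | 20.1% |

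The rate passes 5% when about 2.8 points of all subjects are moved (0.028 × 54 = 1.5 answers). One answer in 54 gives 4.0%.

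**5. Movement from no preference to weekly.**

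| Share of no-preference subjects moved | Answers moved, of 54 | w/d | False-positive rate |
|---|---|---|---|
| 10% | 0.10 × 0.20 × 54 = 1.1 | 42/40 | 3.5% |
| 20% | 2.2 | 44/40 | 4.4% |
| 25% | 2.7 | 45/40 | 5.0% |
| 50% | 5.4 | 50/40 | 9.5% |

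For the same 2.2 answers, reversals give 7.0% and swayed undecided subjects give 4.4%.

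**6. Dependence on the null split.** A 5-point daily-to-weekly shift gives 9.3% at 40/40/20, 11.3% at 30/30/40, 9.5% at 45/45/10 and 6.0% at 50/50/0.

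**The case against.** **The investigator as interviewer is an inference.** Section 9.1.7 names nobody, its heading calls the instrument a questionnaire, and 15.7.2 speaks of subjects answering questionnaires. Section 12.1 does not list the preference answer among items entered directly on the CRF, which hints at a separate source record. The rule in 9.1 is general and qualified. This stands as a limit on certainty. Even so, interview is the only mode stated, and the investigators are the only people named as collecting data.

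**A reader might infer that the investigator settles the next treatment.** Section 9.3.3 does not support that. The subject chooses, and the investigator decides only when the subject cannot.

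**A reader might also infer that the test's error rate is in fact inflated, or inflated toward weekly.** The documents give no evidence of any influence, its size or its direction. A push toward daily would instead cost power to show a weekly preference. Fisher's test is conservative, so very small shifts stay within 5%. Undecided subjects may be easier to sway than those with a stated preference, and moving them does less harm.

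**Part of this is inherent.** A subject cannot compare weekly with daily dosing while blinded to frequency. Asking when the choice is real gives the answer consequence. Both points are fair, but neither requires the answer to be spoken to the treating clinician or taken after the discussion.

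**Conclusion.** The point holds as an unguarded risk of bias in the sole primary endpoint, not as an error shown to have occurred. The documents establish an open-label design, an interviewed answer, a next-treatment decision at the same visit, and no protection of order or privacy. That the treating investigator asks the question is the default reading, not an explicit statement.

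On the assumed null of 40/40/20 with 27 per sequence, about two systematic one-way reversals in 54 raise the false-positive rate from 3.2% to 7.0%, and about four raise it to 20.1%. Two undecided subjects swayed leave it at 4.4%. These figures show how sensitive the test is; they do not estimate the bias. The change is worth making because it is cheap and because no planned analysis could detect or correct the problem.

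**What to change.** In Protocol 9.1.7 and 9.3.3, replace the interview with self-completion:

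- The subject completes the four-option question alone on paper, before any discussion of post-study treatment.
- The subject hands the form to site staff other than the treating investigator.
- Those staff check that exactly one box is ticked and transcribe the answer. The form is kept as the source document. It should not be sealed, since staff must be able to check it.
- The CRF signature required by 12.1 is unaffected, because it comes after the answer is fixed.
- SAP 5.1.1 and 5.2.1, which define the analysis set by interview, should be reworded to match.

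The cost is a one-question form and a sentence on visit order. No visit or sample size is added, and existing site staff can handle the form. The downside is an occasional form handed back for completion. The four options, the test and the clinical rules in 9.3.3 stay as they are.

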### 9.1.8 DTSQ

Subjects will answer the DTSQ (all 8 questions) regarding the diabetes therapy being conducted at each assessment time point during the treatment period. The investigator will instruct the subjects to answer all questions truthfully and record the answer of each question of the DTSQ (8 questions in total) on the CRF.

### 9.1.9 Procedure for Clinical Laboratory Samples

All samples will be collected in accordance with acceptable laboratory procedures. Clinical laboratory tests are listed in Table 9.a.

Table 9.a Laboratory tests

---

#### Serum chemistry

---

- HbA1c

The local laboratory will perform laboratory tests. The results of laboratory tests will be returned to the investigator, who is responsible for reviewing and filing these results.

#### **9.1.10 Pregnancy**

When a subject or a partner of subject was found to be pregnant during the study period, the investigator should notify the monitoring staff of the sponsor. The investigator should provide detailed information using the Follow-up Form for Pregnancy separately wherever possible.

#### **9.1.11 Record of Subjects Who are Withdrawn Before Start of Administration**

A CRF shall be created for all subjects who sign the consent form and are then withdrawn before start of administration.

The following items are to be recorded on the CRF:

- Date of informed consent signature
- Date of birth (or the age at the time of informed consent)
- Gender
- Eligibility
- Reason for withdrawal

The primary reason for withdrawal before start of administration shall be recorded on the CRF according to the following classification:

- Did not meet inclusion criteria or did meet exclusion criteria
- Significant protocol deviation
- Lost to follow-up
- Voluntary withdrawal <specify reason>
- Study termination
- Pregnancy
- Others <specify the reason>

Subject identification numbers assigned to subjects withdrawn from the study before start of administration should not be reused.

### **9.2 Monitoring Subject Treatment Compliance**

The investigator will confirm treatment compliance of study drug at every visit.

Treatment compliance will be classified into 4 categories, as follows: “took the drug properly ( $\geq 90\%$ ),” “usually took the drug ( $\geq 70\%$ ),” “took the drug more than half of the time of dosing ( $\geq 50\%$ ),” and “took the drug less than half of the time of dosing ( $< 50\%$ ).”

### 9.3 Schedule of Observations and Procedures

The schedule for all study-related procedures for all evaluations is shown in Appendix A. Assessments should be completed at the designated visit/time points.

#### 9.3.1 Start of Administration (VISIT 1: Week 0)

After acquisition of informed consent, a physical examination and tests for screening will be performed. Eligibility of subjects will be determined in accordance with the inclusion and exclusion criteria as described in Section 7.0.

An eligible study subject will be randomized in accordance with section 8.2 and starts to be administered trelagliptin or alogliptin.

Tests, observations and evaluations performed at the start of the screening period (Visit 1: Week 0) are shown below.

- Informed consent\*
- Inclusion/exclusion criteria
- Physical examination
- Concomitant medication(a)
- HbA1c
- Demographics, medication history
- Height / weight / BMI
- Concurrent medical conditions
- Prescription of study drug
- DTSQ

\*Informed consent shall be obtained prior to any other tests, observations and evaluations.

(a) Record all concomitant medications

#### 9.3.2 Switch of Study drug (VISIT2: Week 8)

As described in Section 8.4, the preceding drug is switched with the following drug. The study subjects then starts to be administered with the following drug.

Tests, observations and evaluations performed during the treatment period (Visit 2: Week 8) are shown below.

- Physical examination
- HbA1c
- Treatment compliance
- Concomitant medication(a)
- Prescription of study drug
- DTSQ

### 9.3.3 End of Study (VISIT3: Week 16)

The study subjects choose either trelagliptin or alogliptin, or neither of them. If the subjects cannot choose either of them, then the investigators choose the drug for consequent treatment upon adequate explanation.

Tests, observations and evaluations performed at the start of the screening period (Visit 3: Week 16) are shown below.

- Physical examination
- HbA1c
- DTSQ
- Concomitant medication (a)
- Treatment compliance
- Questionnaire for patient preference for treatment

### 9.3.4 Discontinuation

Tests, observations and evaluations performed at the discontinuation are shown below.

- Physical examination
- HbA1c
- DTSQ
- Concomitant medication (a)
- Treatment compliance
- Questionnaire for patient preference for treatment

## **10.0 ADVERSE EVENTS**

### **10.1 Definitions**

#### **10.1.1 AEs**

An AE is defined as any untoward medical occurrence in a subject administered a pharmaceutical product (including the study drug). It does not necessarily have to have a causal relationship with this pharmaceutical product (including the study drug).

An AE can therefore be any unfavorable and unintended sign (e.g., a clinically significant abnormal laboratory value), symptom, or disease temporally associated with the use of a pharmaceutical product (including the study drug) whether or not it is considered related to the pharmaceutical product (including the study drug).

#### **10.1.2 Additional Points to Consider for AEs**

An untoward finding generally may:

- Indicate a new diagnosis or unexpected worsening of a pre-existing condition. (Intermittent events for pre-existing conditions or underlying disease should not be considered AEs.)
- Necessitate therapeutic intervention.
- Require an invasive diagnostic procedure.
- Require discontinuation or a change in the dose of the study drug, or concomitant medication.
- Be considered unfavorable by the investigator for any reason.

Diagnosis vs signs and symptoms:

Each event should be recorded to represent a single diagnosis. Accompanying signs (including abnormal laboratory values or ECG findings) or symptoms should NOT be recorded as additional AEs. If a diagnosis is unknown, sign(s) or symptom(s) should be recorded appropriately as an AE(s).

Laboratory values and ECG findings:

Changes in laboratory values or ECG findings are only considered to be PTEs or AEs if they are judged to be clinically significant (ie, if some action or intervention is required or if the investigator judges the change to be beyond the range of normal physiologic fluctuation). A laboratory or ECG re-test and/or continued monitoring of an abnormal value or findings are not considered an intervention. In addition, repeated or additional noninvasive testing for verification, evaluation or monitoring of an abnormality is not considered an intervention.

If abnormal laboratory values or ECG findings are the result of pathology for which there is an overall diagnosis (eg, increased creatinine in renal failure), the diagnosis only should be reported appropriately as an AE.

Pre-existing conditions (a disease or symptom that is present at the start of study drug administration):

Pre-existing conditions are considered concurrent medical conditions and should NOT be recorded as AEs. However, if the subject experiences a worsening or complication of such a concurrent medical condition, the worsening or complication should be recorded appropriately as an AE (worsening or complication occurs after start of study drug). Investigators should ensure that the event term recorded captures the change in the condition (eg, "worsening of...").

If a subject has a pre-existing episodic concurrent medical condition (eg, asthma, epilepsy) any occurrence of an episode should only be captured as an AE if the condition becomes more frequent, serious or severe in nature. Investigators should ensure that the AE term recorded captures the change in the condition from baseline (eg "worsening of...").

Worsening of AEs:

If the subject experiences a worsening or complication of an AE after any change in study drug, the worsening or complication should be recorded as a new AE. Investigators should ensure that the AE term recorded captures the change in the condition (eg, "worsening of...").

Changes in intensity of AEs:

If the subject experiences changes in intensity of an AE, the event should be captured once with the maximum intensity recorded.

Preplanned procedures (surgery or interventions):

Preplanned procedures (surgeries or therapies) that were scheduled prior to signing of informed consent are not considered AEs. However, if a preplanned procedure is performed early (eg, as an emergency) due to a worsening of the pre-existing condition, the worsening of the condition should be recorded as an AE. Complications resulting from any planned surgery should be reported as AEs.

Elective surgeries or procedures:

Elective procedures performed where there is no change in the subject's medical condition should not be recorded as AEs, but should be documented in the subject's source documents. Complications resulting from an elective surgery should be reported as AEs.

Insufficient clinical response (lack of efficacy):

Insufficient clinical response, efficacy, or pharmacologic action, should NOT be recorded as an AE. The investigator must make the distinction between exacerbation of pre-existing illness and lack of therapeutic efficacy.

Overdose:

Cases of overdose with any medication without manifested side effects are NOT considered AEs,

but instead will be documented on an Overdose page of the CRF. Any manifested side effects will be considered AEs and will be recorded on the AE page of the CRF.

### 10.1.3 SAEs

An SAE is defined as any untoward medical occurrence that at any dose:

- Results in death,
- Is life threatening\* ,
- Requires inpatient hospitalization or prolongation of existing hospitalization,
- Results in persistent or significant disability/incapacity,
- Leads to a congenital anomaly/birth defect,
- Is an important medical event that may expose the subject to danger even though the event is not immediately life-threatening or fatal does not result in hospitalization, or requires intervention to prevent items 1 through 5 above. In addition, event or synonym described in the Takeda Medically Significant Adverse Event List (Table 10.a) is included in this section.

\* The term “life threatening” refers to an event in which the subject was at risk of death at the time of the event; it does not refer to an event that hypothetically might have caused death if it were more severe.

Table 10.a Takeda Medically Significant Adverse Event List

Acute respiratory failure/acute respiratory distress syndrome (ARDS)	Hepatic necrosis
Torsades de pointes/ ventricular fibrillation/ventricular tachycardia	Acute hepatic failure
Malignant hypertension	Anaphylactic shock
Convulsive seizure (including convulsion and epilepsy)	Acute renal failure
Agranulocytosis	Pulmonary hypertension
Aplastic anemia	Pulmonary fibrosis (including interstitial pneumonia)
Toxic epidermal necrolysis/ Oculomucocutaneous syndrome (Stevens-Johnson syndrome)	Neuroleptic malignant syndrome/ malignant hyperpyrexia
	Spontaneous abortion/ stillbirth and fetal death
	Confirmed or suspected transmission of infection by a medicinal product
	Confirmed or suspected endotoxin shock

### 10.1.4 Intensity of AEs

The different categories of intensity (severity) are characterized as follows.

Mild	The event is transient and easily tolerated by the subject.
Moderate	The event interrupts the subject's usual activities.
Severe	The event causes considerable interference with the subject's usual activities.

### 10.1.5 Causality of AEs

The relationship of each AE to the study drug will be assessed using the following categories.

Related	An AE that follows a temporal sequence (including clinical course after discontinuation), or an AE in which there is at least a reasonable probability that a causal relationship to the study drug cannot be ruled out, although other factors such as underlying disease, complications, or concomitant drugs/treatment are also suspected.
Not related	An AE that does not follow a temporal sequence from administration of the study drug or comparative drug. Very likely due to other factors such as underlying disease, complications, or concomitant drugs/treatment.

